08.04.2025

RESEARCH PROTOCOL

ULTRASOUND-GUIDED BILATERAL ERECTOR SPINACH PLANE BLOCK FOR POSTOPERATIVE PAIN IN PEDIATRIC TETHERED CORD SYNDROME SURGERY: A PROSPECTIVE, RANDOMIZED CONTROLLED STUDY

Contents

1. Introduction
2. Aim
3. Hypothesis
4. Phase and Nature of the Study
5. Study Population
6. Inclusion Criteria
7. Exclusion Criteria
8. Study Center
9. Study Duration
10. Materials and Methods
11. Research Budget
12. Ethics Committee Approval
13. Statistics
14. References

1. Giriş

Tethered cord syndrome is a developmental anomaly of neuroaxis characterized by stretching of the spinal cord. It is frequently seen and diagnosed in the pediatric age group due to the presence of many accompanying skin findings (meningocele, meningomyelocele, hypertrichosis, dermal sinus tract, subcutaneous lipoma, etc.). Surgical release of the tight and bound filum terminale is performed. Intraoperative neurophysiological monitoring (IONM) is used to preserve functional nerve tissue and prevent postoperative neurological deficits. Total intravenous anesthesia (TIVA-TCI) with propofol and remifentanil is used to ensure accurate measurements.

Postoperative pain is acute pain caused by surgical trauma and signal transmission in afferent neurons. Pediatric postoperative pain is associated with adverse behaviors, prolonged hospital stay,

and impaired functional recovery. Despite good progress in pain management, ineffective postoperative pain management in children remains a global problem. Regional anesthesia is increasingly used in pediatric patients to provide postoperative analgesia and support intraoperative anesthesia. Ultrasound-guided erector spinae plane block (ESPB) is a new approach. First introduced in 2016 by Forero et al., ESPB is a novel regional anesthesia technique that blocks branches of spinal nerves by injecting a local anesthetic into the fascial plane between the erector spinae muscle and the transverse process. Although new, ESPB has become quite popular due to its ease of application and reliability as a relatively superficial block. Initially, ESPB was defined for chronic pain from the thoracic region. Later, its indications expanded and it is now used in both acute and chronic pain conditions. Applications have also been reported in the lumbar, cervical, and sacral regions, respectively. In recent years, an increasing number of randomized controlled trials (RCTs) have reported that it provides effective postoperative analgesia for thoracic surgeries, nephrectomy, inguinal hernia repair, and laparoscopic cholecystectomy operations in children. In our study, we planned to evaluate the effect of bilateral ESPB on intraoperative anesthetic drug consumption and postoperative pain score and analgesia requirement in pediatric patients operated on due to tethered cord syndrome.

2. Objective

In our study, we aimed to reduce intraoperative anesthetic drug consumption and the level of pain in the first 24 hours postoperatively, the need for analgesics, and unwanted side effects related to analgesics by applying bilateral ESPB in pediatric patients operated on due to tethered cord syndrome.

3. Hypothesis

Bilateral ESPB reduces intraoperative anesthetic drug consumption and the need for postoperative analgesia in pediatric patients operated on due to tethered cord syndrome.

4. Study Phase and Nature

Low-risk scientific study - Prospective randomized controlled single-blind clinical trial

5. Study Population

Pediatric patients undergoing surgery for elective tethered cord syndrome

6. Inclusion Criteria

- Patients whose parents consented to participate in the study
- Patients aged 18 and under
- ASA (American Society of Anesthesiologists) physical status I, II, and III
- Pediatric patients undergoing elective tethered cord syndrome surgery

7. Exclusion Criteria

- Patients whose parents did not consent to participate in the study

- Patients with ASA physical status IV and V

- Use of anticoagulant medications

- Allergy to local anesthetic drugs

- Patients with a history of gastrointestinal bleeding

- Patients with infection in the area where the block is planned

8. Study Center

Health Sciences University Bursa High Specialization Training and Research Hospital Anesthesiology and Reanimation Clinic

9. Study Duration

1 year

10. Material – Method

Patients included in the study will be divided into 2 groups according to the randomized (closed envelope) sampling method; Erector Spina Plane Block (ESPB, n=34) group and Control group (CG, n=34). Patients who regularly take medication due to cardiovascular or other systemic diseases will continue their medication. Those whose coagulation parameters are checked before the operation and are normal will be included in the study.

The patients' age, height, weight, gender, additional diseases, ASA scores, operation and anesthesia duration, operation level, level of block performed in the group undergoing ESP block, and total anesthetic drug consumption will be recorded. Standard ECG, SpO₂, non-invasive blood pressure (invasive blood pressure monitoring in necessary cases), EtCO₂ and BIS monitoring will be applied in the operating room. After appropriate intravenous access is established in both groups of patients, anesthesia induction will be achieved with 2 mg/kg propofol (Propofol 2%®, FreseniusKabi, Melsungen, Germany), 1 µgr/kg fentanyl (Fentanyl Citrate®, Hospira, USA), and 0.6 mg/kg rocuronium (Esmeron®, Organon, Kloosterstraat, Netherlands). Following intubation, anesthesia maintenance will be administered with a 2 l/min flow rate of 50/50 O₂/air mixture. Inhalation anesthetics will not be used, and no additional doses of muscle relaxants will be given. Neuromonitoring will be performed on all patients by the neurosurgical team following intubation. Patients will be turned to the prone position once they are stable. For total intravenous anesthesia in patients undergoing neuromonitoring-based anesthesia maintenance, propofol will be infused at an initial target plasma concentration of 2.5-4 µg.ml⁻¹ (Medcaptain Shenzhen, Guangdong, CHINA, Elevated model FK/FD). Remifentanil (ULTIVA®, GlaxoSmithKline Parma, Italy) will be infused at a rate of 0.5-1 µg/kg/min. Infusions will be maintained to maintain a BIS of 40-60. Preoperative,

peroperative 5th, 10th, 15th, 30th, 60th, 90th, 120th, 180th minute, and post-extubation heart rate, supravascular pressure, intravascular pressure, SpO₂, ETCO₂, and BIS values will be recorded.

Patients will be randomly assigned to two separate groups using a sealed envelope method, regardless of their demographic and surgical characteristics. In the ESP Block group, with the patient in the prone position, the research anesthesia team, following aseptic and antiseptic rules, will insert a linear probe (Hitachi Aloka Prosound F31) with a depth of 2-4 cm and a frequency of 10-15 mHz, approximately 2-3 cm lateral to the spinous process, one level above the operative level, in the parasagittal plane, under USG guidance (Hitachi Aloka Prosound F31). After visualizing the transverse process using an in-plane approach, a 50 mm long block needle (Braun Stimuplex® D 0.22 Gax2 in.50mm, Braun, Germany) will be inserted through the skin, passing through the trapezius and erector spinae muscles. When the needle reaches the transverse process (approximately 2-3 cm deep), a test dose of 0.5-1 mL of 0.9% NaCl will be administered between the erector spinae fascia and the vertebral transverse process to confirm the needle's position. After the fascia is seen to be open, a local anesthetic volume of 0.5% bupivacaine (Buvasin, VEM Pharmaceuticals, Turkey) will be calculated as 2 ml per vertebral pressure, not exceeding a maximum dose of 2 mg/kg. This total volume will be diluted half and half with 0.9% NaCl solution to prepare a 0.25% bupivacaine concentration. The calculated local anesthetic solution will be administered to the erector spinae area for ESPB. The same procedures will be performed on the opposite side. No procedure will be performed on the control group. Both groups will receive 15 mg/kg Paracetamol (Parol®, ATABAY, Kurtköy, Pendik, İstanbul) intravenously 20 minutes before the end of surgery. After surgery, patients will be decurarized with 2 mg/kg IV sugammadex (Bridion, MerckSharpDohme, New Jersey, USA), extubated, and taken to the recovery unit. After being admitted to the recovery room, both groups will be assessed using the Wong-Baker FACES™ Pain Rating Scale for children under 5 years old and the FLACC: Pain Rating Scale for children 5 years and older, with pain scores at 0, 5, 10, 15, and 20 minutes. Patients with scores >5 will receive 0.5 mcg/kg fentanyl (TALİNAT®, VEM İlaç, Kapaklı/TEKİRDAG) for rescue analgesia. Paracetamol 15 mg/kg/6 hours will be administered intravenously for postoperative analgesia. A blinded investigator will assess patients' pain scores, analgesic requirements, names of analgesics administered, and nausea/vomiting at 30 minutes, 1, 2, 4, 6, 12, and 24 hours postoperatively. The time and dose of the first postoperative analgesic, and length of hospital stay will be recorded.

11. Research Budget

The cost of 34 block needles and 34 doses of the drug buvasin containing the active ingredient bupivacaine for one patient has been submitted with a propharmaceutical invoice. The expenses will be covered by the researchers.

12. Ethics Committee Approval

An application has been submitted for ethics committee approval.

13. Statistics

Statistical analyses of the obtained data will be performed using the IBM SPSS Statistics 21.0 software package. Descriptive statistics of the data will include mean, standard deviation, frequency, and percentage values. Chi-square and FischerExact tests will be used for the analysis of categorical variables. The normality assumption of continuous numerical variables will be checked separately in groups using the Shapiro-Wilk test. Analysis of variance (ANOVA) will be used for independent group

comparisons of numerical variables showing normal distribution. Kruskal-Wallis (KW) test will be used for variables that do not show normal distribution. For comparisons of consecutive measurements, the Wilcoxon Signed Ranks test will be used for pairs of measurements, the Friedman test for more than two measurements, and the Pearson correlation test will be used as a correlation test. The significance level will be set at $p<0.05$ in all analyses. The required sample size for the study was calculated as 68 (34+34) patients in total, including the group that underwent ESPB and the group that did not undergo ESPB, with an effect size of 0.70, 80% test power, and 95% confidence level. The relevant calculations were made in the G-Power 3.1.9.2 software package.

14. References

1. Gado, A. A., Alsadek, W. M., Ali, H., & Ismail, A. A. (2022). Erector spinae plane block for children undergoing cardiac surgeries via sternotomy: a randomized controlled trial Anesth Pain Med. 2022;12(2):e123723. doi: 10.5812/aampm-123723. PMID: 35991776
2. Aksu, C., & Gürkan, Y. (2018). Ultrasound guided erector spinae block for postoperative analgesia in pediatric nephrectomy surgeries. J Clin Anesth. 2018 Mar;45:35-36 doi: 10.1016/j.jclinane.2017.12.021. Epub 2017 Dec 20. PMID: 29274546

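### The side-effect objective can be addressed only for nausea and vomiting, and no block-related harm is prespecified

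*Combined protocol and SAP*

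**What the plan says.** Section 2 lists, among the aims, fewer "unwanted side effects related to analgesics". It does not say which effects are meant. The hypothesis in Section 3 leaves them out: "Bilateral ESPB reduces intraoperative anesthetic drug consumption and the need for postoperative analgesia".

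Section 10 has the blinded investigator record pain scores and analgesic requirements, together with "names of analgesics administered, and nausea/vomiting at 30 minutes, 1, 2, 4, 6, 12, and 24 hours postoperatively". Nausea/vomiting is the only side effect named. About the block, the plan records its level: "level of block performed in the group undergoing ESP block, and total anesthetic drug consumption will be recorded". Physiological readings are taken before and during surgery and once afterwards, ending with "post-extubation heart rate, supravascular pressure, intravascular pressure, SpO₂, ETCO₂, and BIS values will be recorded". The remaining late items are these: "The time and dose of the first postoperative analgesic, and length of hospital stay will be recorded".

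The contents list has no safety or adverse-event section. Section 13 (Statistics) provides chi-square and Fisher tests for categorical variables in general and names no side-effect or complication analysis.

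**The concern.** Both arms receive opioids: fentanyl at induction, a remifentanil infusion, and fentanyl as rescue if needed. Sedation, respiratory depression and itching are therefore effects that fewer analgesics might reduce, yet none of them is recorded.

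The block is an added needle procedure on both sides of the spine, and controls receive no procedure, so any harm from it falls on one arm. The protocol itself anticipates such harm. Section 7 excludes anticoagulant use, local anaesthetic allergy and infection at the planned site, while Section 10 requires normal coagulation and caps the local anaesthetic dose. It guards against bleeding, toxicity and infection without recording whether they occur.

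What is at stake is a report that gives the benefit of the injection with no defined account of its complications. Data that were not collected cannot be recovered at analysis.

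**Working it through.** **1. Objective against data collected.**

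| Item | Recorded? | Where |
|---|---|---|
| Nausea/vomiting | Yes, blind, both arms, 7 times (30 min to 24 h) | Section 10 |
| Sedation, respiratory depression, itching | No | – |
| Block level | Yes, ESPB arm | Section 10 |
| Vascular puncture, haematoma, local anaesthetic toxicity, block failure | No | – |
| New leg weakness | No | – |
| Heart rate, pressures, SpO₂, ETCO₂, BIS | Yes, to just after extubation; not defined as safety outcomes | Section 10 |

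**2. The plan's own sample size.** Inputs from Section 13: effect size 0.70, 80% power, 95% confidence. I read the effect size as a standardised mean difference and assume a two-sided 5% test, since the plan states neither. A two-sample t-test then needs 33.02 patients per arm, rounded up to 34, which gives 2 × 34 = 68. This matches the plan. The calculation concerns a continuous outcome and does not cover a comparison of side effects.

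**3. What 34 per arm can say about nausea/vomiting.** The documents give no event rates, so I assume control rates p₁ of 20% to 50%, halved to p₂ under ESPB. With p̄ = (p₁ + p₂)/2:

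power = Φ{ [ |p₁ − p₂|√n − 1.96√(2p̄(1 − p̄)) ] / √(p₁(1 − p₁) + p₂(1 − p₂)) }

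For 20% against 10%: (0.10 × 5.831 − 1.96 × 0.505)/0.500 = −0.813, and Φ(−0.813) = 20.8%. Fisher power comes from enumerating all possible tables.

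| Control → ESPB | Chi-square power | Fisher power | n per arm for 80% (chi-square) |
|---|---|---|---|
| 20% → 10% | 20.8% | 12.2% | 199 |
| 30% → 15% | 31.3% | 22.3% | 121 |
| 40% → 20% | 43.5% | 34.1% | 82 |
| 50% → 25% | 57.0% | 49.3% | 58 |

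Even the one side effect that is recorded would be compared with low power across this range.

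**4. What recording block events would give.** With 0 events in n = 34 ESPB patients, the exact upper limit is 1 − α^(1/n):

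- two-sided 95%: 1 − 0.025^(1/34) = 10.3%
- one-sided 95%: 1 − 0.05^(1/34) = 8.4%

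These limits are per patient. Each patient has an injection on both sides, so they are not rates per injection.

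The chance of seeing at least one event is 1 − (1 − r)^34. It is 28.9% at a true rate r of 1%, 49.7% at 2% and 82.5% at 5%.

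**The case against.** The case for leaving the plan alone has several parts.

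- **The objective names no particular effect.** Nausea/vomiting is a genuine analgesic side effect, assessed blind and often. A reader might infer that the trial cannot answer its side-effect objective at all. The documents do not support that, because the objective is partly addressed.
- **Side effects are peripheral.** The hypothesis omits them. That is true, and it makes narrowing the objective a legitimate alternative. It does not deal with block complications, which are a separate gap from analgesic side effects.
- **Some safety information exists.** Vital signs are recorded, all patients have neuromonitoring, and length of stay is noted. A reader might infer that nothing bearing on harm is collected, which would go too far. But none of these is defined as a safety outcome, and no vital sign is scheduled in the 30 min to 24 h period.
- **Clinicians will note serious events anyway.** The documents do not say so, and notes without set definitions or times are a poor basis for comparing arms.
- **The trial is too small to establish safety.** This stands, as step 4 of the working shows.
- **Extra fields could do damage.** This also stands if they are badly placed. A blinded assessor who inspects for haematoma or asks about puncture may learn the allocation and so compromise the pain scores. Puncture cannot occur in controls and belongs to the time of the procedure. Leg weakness cannot be interpreted without a baseline, since the surgery can also cause it. The fix has to respect all three.

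**Conclusion.** The point holds in a limited form. The side-effect aim in Section 2 can be addressed only for nausea/vomiting, and no harm from the block is prespecified. Both follow directly from the text and need no assumption.

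The sample size of 68 reproduces and is not in question here. The power figures for nausea/vomiting (12% to 57% across both tests) rest on assumed control rates, an assumed halving and two-sided testing.

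A reader might also infer that adding the fields would let the trial weigh harm against benefit conclusively. It would not. No events in 34 patients would still be compatible with a complication rate of about 10% (two-sided limit), and an event with a true rate of 1% would more likely than not go unseen. The case for the change is that a wide interval can be reported, whereas with no recording there is none.

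**What to change.** Before enrolment, add the following to Section 10, each item with a short definition fixed in advance and usable across the age range:

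1. **Analgesic side effects, both arms.** The blinded investigator records sedation, respiratory depression and itching at the existing 30 min to 24 h assessments.
2. **Block events, ESPB arm.** The block operator, not the blinded assessor, records vascular puncture, signs of local anaesthetic toxicity and block failure at the procedure. Because the patient is anaesthetised at that point, block failure needs a technical definition. Unblinded clinical staff record any injection-site haematoma.
3. **New leg weakness, both arms.** Record it in the same way in each arm, against documented preoperative neurological status.

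In Section 13, state that these will be reported descriptively as counts by arm with exact two-sided 95% confidence intervals. State the zero-event limit for 34 ESPB patients and say that it is not evidence of safety.

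If item 1 is not adopted, narrow the Section 2 objective to nausea/vomiting. That would align the objective with the data but leave block harms unrecorded, so items 2 and 3 are worth adding either way.

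The cost is slightly longer records, plus care to keep block-site findings on a separate form that the blinded assessor does not see. No extra visits, procedures, staff or patients are needed.

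### Preoperative pain and regular analgesic, neuropathic-pain or antiepileptic drug use are neither recorded nor adjusted for, which costs precision and hides chance imbalance but does not bias the comparison

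*Combined protocol and SAP*

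**What the plan says.** **Eligibility.** Section 6 admits "Pediatric patients undergoing elective tethered cord syndrome surgery", aged 18 or under, ASA I to III, with parental consent. In section 7 the only exclusion for taking a drug is "Use of anticoagulant medications". Neither section mentions existing pain, or analgesic, neuropathic-pain or antiepileptic treatment.

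**Regular medication.** Section 10 has one sentence on it: "Patients who regularly take medication due to cardiovascular or other systemic diseases will continue their medication". It is limited by indication and names no drug class.

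**What is recorded.** The baseline list in section 10 begins "The patients' age, height, weight, gender, additional diseases, ASA scores, operation and anesthesia duration, operation level" and goes on to block level and total anesthetic consumption. The series of measurements that starts preoperatively ends with "post-extubation heart rate, supravascular pressure, intravascular pressure, SpO₂, ETCO₂, and BIS values will be recorded". Neither list contains a pain score or a drug history. Pain scoring begins later: "After being admitted to the recovery room, both groups will be assessed using the Wong-Baker FACES™ Pain Rating Scale", with a second scale for the other age group. Analgesics are recorded only from after surgery: "The time and dose of the first postoperative analgesic, and length of hospital stay will be recorded".

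**Hypothesis and analysis.** Section 3 states that "Bilateral ESPB reduces intraoperative anesthetic drug consumption and the need for postoperative analgesia". Section 10 allocates by sealed envelope without regard to patient characteristics, 34 per arm. Section 13 compares groups with ANOVA or Kruskal-Wallis and names no covariate.

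**The concern.** In a pain trial, pain before surgery and regular use of drugs that act on pain or sedation are obvious candidates for prognostic factors. Both parts of the hypothesis could be affected: anesthetic consumption, because the infusions are run to a BIS target of 40 to 60, and analgesic need, because rescue is triggered by a score above 5. The documents do not themselves say how strongly such drugs act on these outcomes, so any size given here is an assumption.

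If such children fall unevenly between the arms, part of the observed difference will reflect who was in each arm. With neither factor recorded, a reader of the final report could not check for this and the analyst could not allow for it. Variation that a baseline score would explain also stays in the error term and weakens the test.

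**Working it through.** **Inputs from the documents:** 34 per arm, 68 in total (sections 10 and 13); effect size 0.70, 80% power, 95% confidence (section 13). Sidedness is not stated; two-sided 0.05 is assumed.

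**Inputs assumed, because the documents give none:** the number of users, the shift in a user's outcome, and the correlation of a preoperative score with the outcome.

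**1. The plan's own figure.** A two-sample t test (noncentral t) with d = 0.70, two-sided 0.05 and 80% power needs 33.02 per arm, rounded up to 34, or 68 in total. This matches the plan. Power at 34 per arm is 81.2%. There is no arithmetic error here.

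**2. Chance imbalance.** With k users among 68 and 34 per arm, the number of users in one arm is hypergeometric: P(a) = C(k, a) × C(68 − k, 34 − a) / C(68, 34).
- k = 10: P(7) = 0.1107, P(8) = 0.0350, P(9) = 0.0061, P(10) = 0.0005. A 7:3 or worse split in either direction: 2 × (0.1107 + 0.0350 + 0.0061 + 0.0005) = 0.305.
- k = 10, 8:2 or worse: 2 × (0.0350 + 0.0061 + 0.0005) = 0.083.
- k = 14, 9:5 or worse: 0.369.

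**3. What a split does to the outcome.** If each user's outcome moves by 1 SD, the difference in means moves by (difference in user counts) / 34.
- 7:3 split: 4/34 = 0.12 SD, which is 0.12/0.70 = 17% of the planned effect.
- 8:2 split: 6/34 = 0.18 SD, which is 0.18/0.70 = 25% of it.
- The standard error of the difference is √(2/34) = 0.24 SD. The two shifts are therefore about 0.5 and 0.7 of a standard error.

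**4. Is the test biased?** Simulation of the unadjusted t test with no block effect, random allocation, and a 1 SD shift in 20% or 30% of children (40,000 trials each) gave type I error of 4.95% and 5.13%. It stays nominal.

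**5. Precision lost.** Suppose 0.70 was meant for a population without such children. A share p with shift s SD then lowers the effective effect size to 0.70/√(1 + p(1 − p)s²).
- p = 0.1, s = 0.5: 0.70/√1.0225 = 0.692, power 80.3%.
- p = 0.3, s = 1: 0.70/√1.21 = 0.636, power 73.4%.

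**6. Precision available from adjustment.** Adjusting for a baseline score with correlation r raises the effective effect size to 0.70/√(1 − r²). At 34 per arm:

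| r (assumed) | effective d | power |
|---|---|---|
| none | 0.700 | 81.2% |
| 0.2 | 0.714 | 82.7% |
| 0.3 | 0.734 | 84.6% |
| 0.4 | 0.764 | 87.3% |
| 0.5 | 0.808 | 90.7% |

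**The case against.** The strongest objection is that randomisation already deals with these factors. They are balanced in expectation, and chance imbalance is part of what the 5% error rate covers. Step 4 bears this out, and the objection stands: a reader might infer that prior pain and drug exposure confound both outcomes, and the design does not support that.

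A reader might also infer that children on analgesic or anticonvulsant drugs are told to continue them. The sentence does not say so. An antiepileptic given for a coexisting disease could fall under it, but a drug taken for pain from the tethered cord itself is not clearly covered. The rule for such drugs is unstated.

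Third, the effect is small. Even a full 1 SD shift with a 7:3 split moves the result by about half a standard error, and the frequencies of 10 and 14 in 68 have no source in the documents. This stands as a limit on severity.

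Fourth, coexisting diseases and ASA class are recorded, so some of these children could be identified by arm. That holds in part, but neither item gives the drug or the level of pain.

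Finally, one might wish to exclude regular users. Validity does not require it under random allocation. It would narrow the stated population and cost recruitment in a one-year, single-centre study. Rewriting the rule on regular medication would be a matter of clinical management. Neither is supported.

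**Conclusion.** The gap is real and modest. The plan admits children with prior pain or relevant regular drugs, records neither, and adjusts for neither. The comparison remains valid. What is lost is precision, together with the ability to see and allow for chance imbalance at 34 per arm.

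Its size cannot be fixed from the documents. Under the assumed values, a 7:3 or worse split of 10 users occurs in about 30% of trials, and power without adjustment falls to between 80.3% and 73.4%. Against that, adjusting for a preoperative score could raise power from 81% to about 83–91% if its correlation with the outcome is 0.2 to 0.5. If few children have preoperative pain, both the loss and the gain will be small. The case for change rests on its low cost, and on the fact that these items cannot reliably be recovered after surgery.

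**What to change.** 1. **Section 10, baseline list.** Add a preoperative pain score, on the scale that the child will be assessed with postoperatively. Add current regular analgesic, neuropathic-pain and antiepileptic use (yes/no, and which drug). This shows what each child was taking, however the continuation sentence is read.
2. **Reporting.** Show both items by arm in the baseline table.
3. **Section 13, pain.** Compare postoperative pain with a model adjusted for the preoperative score. Include an indicator for the scale used, since section 10 assigns two instruments by age.
4. **Section 13, consumption.** A preoperative pain score may explain little of anesthetic consumption. Add a sensitivity analysis of anesthetic consumption and of analgesic need, adjusted for regular drug use.

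The cost is two baseline items, the adjusted pain model and the sensitivity analysis, with no change in sample size. Eligibility and every child's regular medication stay as they are.

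### One BIS 40-60 band shared by two infusions leaves the remifentanil rate to discretion, and no blinding is described for the person setting it, so a consumption difference is open to expectation bias

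*Combined protocol and SAP*

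**What the plan says.** Sections 2 and 3 name lower intraoperative anaesthetic drug consumption as an aim and a hypothesis, alongside less need for postoperative analgesia.

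Section 10 (Material – Method) gives propofol an initial plasma target of 2.5-4 µg/ml, while remifentanil "will be infused at a rate of 0.5-1 µg/kg/min". Both are then steered by one sentence: "Infusions will be maintained to maintain a BIS of 40-60". Nothing says which drug to change, when or by how much. Heart rate, pressures and BIS are recorded at set times, but none of the haemodynamic values triggers a change.

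The outcome is described only in a list of items to record, where "total anesthetic drug consumption will be recorded". It is not split by drug or scaled to body size or time. Section 6 admits "Patients aged 18 and under", and the same list in Section 10 includes "age, height, weight, gender, additional diseases, ASA scores, operation and anesthesia duration".

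Section 4 calls the trial single-blind. The block is done in theatre by "the research anesthesia team", and controls have neither block nor sham. The only blinded person described is the investigator who assesses patients from 30 minutes after surgery. The plan does not say who runs the infusions.

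**The concern.** An infusion rate is chosen by a clinician, and here the chosen dose is itself a measured outcome. Once BIS is in range, many combinations of propofol and remifentanil comply with the plan, including remifentanil rates that differ two-fold. If the person choosing knows that a block was given and expects it to work, a slightly lower setting in that arm is natural and breaks no rule.

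The resulting difference would look like a block effect. The recorded BIS, heart rate and pressures would only partly separate the two explanations, and the lost information cannot be recovered after data collection. The argument needs no claim about what BIS measures: one target and two free rates are enough.

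**Working it through.** **The plan's own figure.** Section 13 gives 68 patients (34+34) "with an effect size of 0.70, 80% test power" and 95% confidence. A two-sided two-sample t-test at alpha 0.05 with d = 0.70 and 80% power needs 33.02 per arm, rounded up to 34, or 68 in total. Power at 34 per arm is 81.2%. The figure reproduces, and this point does not dispute it. The 0.70 is not tied to consumption, so it says nothing about the SD of that outcome.

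**False-positive rate from discretion alone.** Assume no block effect and a mean remifentanil setting 10% lower in the block arm through discretion. The documents give no SD, so a range is used.

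- Standardised shift: d = 0.10 / (SD as a fraction of the mean).
- Test: two-sided t-test (for two groups, the same as the planned ANOVA), n = 34 per arm, 66 degrees of freedom, noncentrality = d × √(34/2) = 4.123 × d.

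| Assumed SD, % of mean | d | Trials with p<0.05 |
|---|---|---|
| 20 | 0.10/0.20 = 0.50 | 53% |
| 25 | 0.10/0.25 = 0.40 | 37% |
| 30 | 0.10/0.30 = 0.333 | 27% |
| 40 | 0.10/0.40 = 0.25 | 17% |
| 60 | 0.10/0.60 = 0.167 | 10% |
| 80 | 0.10/0.80 = 0.125 | 8% |

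With no shift the rate is 5%. SDs of 20-30% are taken as plausible for a per-kg, per-time rate, and 60-80% for a total not adjusted for weight and duration across patients up to 18 years. Halving the shift to 5% halves each d and gives 10-17% for the rate and about 6% for the total. If consumption is skewed, Section 13 switches test ("Kruskal-Wallis (KW) test will be used for variables that do not show normal distribution"); the rates above were not recomputed for that test.

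**The 0.5 lower limit.** If the limit is followed literally, a need below 0.5 is delivered as 0.5. For a normally distributed need with mean μ and SD σ, and z = (0.5 − μ)/σ, the mean delivered rate is 0.5·Φ(z) + μ·(1 − Φ(z)) + σ·φ(z). Take an assumed control need of 0.6 and a true 30% fall (block need 0.42):

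- CV 20%: control mean 0.6136, block mean 0.5077; observed fall 1 − 0.5077/0.6136 = 17.3%.
- CV 30%: control mean 0.6326, block mean 0.5201; observed fall 1 − 0.5201/0.6326 = 17.8%.

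A true 30% fall is therefore seen as about 17-18%. Adding the upper limit of 1 leaves this at about 17-18%.

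**The case against.** **The plan does not say that the titrator is unblinded.** True. A reader might infer it from the single-blind label, the block in theatre and the absence of a sham. The documents support only that no blinding of this role is described.

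**The high false-positive rates do not belong to the outcome as written.** This stands. The plan records a total, for which the assumed range gives about 8-10%. The 27-53% range applies to a per-kg, per-time rate that the plan does not define. It also means that moving to the better-scaled measure without a titration rule would make the same bias easier to declare significant.

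**The lower limit could hide the effect.** A reader might infer this, but it would need a typical control need below the range the investigators chose, and nothing in the documents suggests that. At an assumed need of 0.6-0.8, t-test power for a true 30% fall stays at or above 99% with the limit in place: the effect is understated, not lost. The two mechanisms also partly cancel, because discretion can lower a rate only where it is above 0.5. The net direction cannot be given.

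**The postoperative assessor is blinded, so the later outcomes are safe.** The documents do not establish this either. If opioid exposure during surgery differs by arm through expectation, blinding the assessor does not undo it. This point makes no claim about those outcomes in either direction.

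**Heart rate and pressure are imperfect guides.** Fair: Section 10 lets patients continue cardiovascular medication, and the anaesthetic is chosen to suit neuromonitoring. A rule needs room for both.

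**Consumption is one of several outcomes, and the title is about postoperative pain.** True, and it limits the weight of the point. But consumption is in the stated hypothesis.

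**Conclusion.** The point holds. Followed exactly, the plan yields a consumption outcome that is partly set by the discretion of someone whose blinding is not described, so a between-arm difference could partly reflect expectation.

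Its size cannot be set from the documents, which give no rates or SDs for consumption. The false-positive ranges above are conditional illustrations: they rest on the assumed 10% shift and assumed SDs and are not estimates for this trial. Understatement by the 0.5 limit is a secondary matter and depends on an assumed control need. The change should be made, because it is cheap before enrolment and cannot be made afterwards. Confidence is medium.

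**What to change.** 1. **Titration rule (Section 10).** Replace the BIS sentence with one rule used identically in both arms. Propofol is titrated to BIS 40-60. Remifentanil starts at one fixed rate and changes by a fixed step when heart rate or blood pressure departs by a pre-set percentage from baseline. Baseline is taken after turning prone and before the block, at the same time point in controls. The team fixes the values before the first patient, allows for neuromonitoring needs and cardiovascular medication, and logs overrides with reasons.
2. **Analysis and blinding.** Analyse propofol and remifentanil separately, per kg and per unit time, beside BIS, heart rate and blood pressure by arm. Do this together with the rule, not instead of it. Where existing staffing allows, have the infusions run by someone who is out of the room or screened during the block; otherwise describe the consumption result as open-label.
3. **Lower limit.** State in one sentence that the 0.5 limit, if followed literally, can understate a true remifentanil reduction.

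Cost: protocol wording, an override line on the anaesthesia record and one summary table, using monitoring, weight and duration already planned. No extra patients or procedures are needed, and screening the titrator is asked for only where existing staff permit. The anaesthetist loses a little discretion, and some expectation bias remains.
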